## **STUDY DRUG, DOSAGE, AND ROUTE OF ADMINISTRATION:**

### **PB2452:**

PB2452 IV infusion, prepared according to the Pharmacy Manual, will be administered on Day 1 for up to 48 hours. The total dose for each subject will not exceed 30 g. The infusion rate will not exceed 18 g over 30 minutes and the concentration will not exceed 24g in 250mL. Subjects will not receive more than 250 mL of study drug infusion within any 1-hour period.

For each cohort, the dose, infusion rate, and duration will be communicated from the Sponsor to PPD in a Dosing Memo issued prior to initiation of each treatment cohort.

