### **3.4.2 Treatments Administered**

#### **PB2452:**

PB2452 IV infusion, prepared according to the Pharmacy Manual, will be administered on Day 1 for up to 48 hours. The total dose for each subject will not exceed 30g. The infusion rate will not exceed 18g over 30 minutes and the concentration will not exceed 24g in 250mL. Subjects will not receive more than 250 mL of study drug infusion within any 1-hour period.

For each cohort, the dose, infusion rate, and duration will be communicated from the Sponsor to the study site, PPD, in a Dosing Memo issued prior to initiation of each treatment cohort.

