### STUDY DESIGN AND METHODOLOGY:

This is Part B of a two-part Phase 2A, randomized, double-blind, placebo-controlled, single dose, sequential group study to evaluate the safety, tolerability, PK, and PD of PB2452 vs matching placebo. Part A investigated various dose regimens of PB2452 administered intravenously to older (ages 50 to 64 years) and elderly (ages 65 to 80 years) male and female subjects pretreated with ticagrelor + aspirin (ASA) as part of dual antiplatelet therapy. Part B investigates various dose levels and regimens of PB2452 administered to healthy male and female subjects (ages 18-50) pretreated with a high dose of ticagrelor alone (180 mg) twice daily (BID). Part A is described in a separate protocol document.

In Part B described herein, up to 3 dose levels and/or administration regimens of PB2452 will be evaluated in up to 3 cohorts. Each cohort will include up to 12 subjects randomized in a 3:1 ratio (PB2452:placebo). All references to study drug within the content of the protocol apply to PB2452 or matching placebo.

This initial cohort of Part B will include healthy subjects pretreated with 180 mg of oral ticagrelor twice daily for 48 hours prior to randomization to a dose and regimen of PB2452 (or matching placebo) described in a cohort-specific Dosing Memo. The written Dosing Memo provided by the Sponsor to the clinical site will include details of the dosing regimen, cohort size, sampling schedules, and other cohort-specific study activities prior to initiation of each cohort. The dose level of the initial regimen in Part B will not exceed twice the total dose level (36 g) shown to be safe and well tolerated in older and elderly subjects (50-80 years) in Part A of this Phase 2A study and in the Phase 1 study of PB2452 in healthy subjects (PB2452-PT-CL-0001).

Following completion of Cohort 3, subsequent cohort(s) may test the same, higher or lower dose levels, and/or different infusion regimens of PB2452 or matching placebo as determined by the Sponsor after examination of available PD and safety data from the prior cohort(s) and described in a subsequent Dosing Memo. Duration of study drug infusions will not exceed 48 hours.

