### **3.4.2 Treatments Administered**

#### **PB2452:**

PB2452 IV infusion, prepared according to the Pharmacy Manual, will be administered on Day 1 for up to 48 hours. For each cohort, the dose, infusion rate, and duration will be communicated from the Sponsor to the study site, PPD, in a Dosing Memo issued prior to initiation of each treatment cohort.

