### **3.4.6 Treatment Compliance**

All doses of study drug, matching placebo, and ticagrelor will be administered at the clinical site under direct observation of clinic personnel and recorded in the eCRF.

The date, time, and actual dose received of study drug and matching placebo infusion and ticagrelor dosing will be recorded on the appropriate pages of the eCRF. If a subject was scheduled to receive any of these drugs and did not, the reason for the missed or partial dose will be recorded in the eCRF pages.

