3.1. Overall Study Design and Plan

This is a Phase 2A, randomized, double-blind, placebo-controlled, single dose, sequential group study. Part A evaluates the safety, tolerability, PK and PD of PB2452 vs matching placebo with ticagrelor + ASA pretreatment when various dose levels and administration regimens are administered to 1) healthy older (age 50 to 64 years) and elderly (age 65 to 80 years) male and female subjects in Part A. Part B investigates various dose levels and regimens of PB2452 administered to healthy male and female subjects (ages 18-50) pretreated with a high dose of ticagrelor alone (180 mg) twice daily (BID).. All references to study drug within this SAP apply to PB2452 or matching placebo. Part B evaluates the safety, tolerability, PK and PD of PB2452 vs matching placebo with High Dose of ticagrelor + ASA pretreatment to healthy male and female subjects. All references to study drug within this SAP apply to PB2452 or matching placebo.

Each cohort was planned to include approximately 8 to 12 subjects randomized in a 3:1 ratio, PB2452:placebo.

PART A:

The initial cohort (Cohort 1) included approximately 8 subjects ages 50 to 80 years pretreated with ASA + ticagrelor randomized to 18 grams (g) of PB2452 or matching placebo administered as an initial 6 g bolus infused over 10 minutes, followed by 12 g infused over the next 15 hours and 50 minutes to complete a 16 hour administration regimen.

Following completion of Cohort 1, a subsequent cohort was tested, also at an 18 g dose level of PB2452 or matching placebo in the same population as in Cohort 1. A written Dosing Memo was provided by the Sponsor to the clinical site describing details of the dosing regimen, cohort population, cohort size, sampling schedules, and other cohort-specific study activities prior to initiation of each cohort. The maximum total dose of PB2452 administered to any subject as not to exceed 30g. Duration of study drug infusions was not to exceed 48 hours. The maximum administration rate of PB2452 was not to exceed 18g over 30 minutes.

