The study consisted of a Screening period (Days -45 to -4), a Check-in day (Day -3) and Pretreatment Period, an on-site Randomization/Treatment day (Day 1), 3 days on-site for treatment and safety monitoring, a Follow-up Visit (Day 7), and a Final Follow-up visit (Day 28 [± 2 days]). Seven days prior to Randomization (Day -7), subjects were administered ASA 81 mg orally once daily (QD) until the final dose on the morning of Day 1 before receiving study drug. A ticagrelor 180 mg oral loading dose was administered on the morning of Day -2 followed by 90 mg every 12 hours until the 5th dose was administered on the morning of Day 1. After completion of Cohort 1, the Sponsor had the choice to have a 6th dose of ticagrelor administered 24 hours after the initiation of study drug in a subsequent cohort.

Subjects checked into the clinical site (PPD) on Day -3. In the morning on Day -2, subjects began pretreatment with ticagrelor as described in the preceding paragraph. On Day 1, subjects who met all the inclusion criteria and none of the exclusion criteria were randomized in a ratio 3:1 (PB2452:placebo), to receive an IV dose of PB2452 or placebo 2 hours following the 5th ticagrelor dose. Subjects may have been discharged from the clinical site between Days 3 and 7 inclusive to return for a Follow-up visit on Day 7, if already discharged, and on Day 28 (± 2 days).

Safety and tolerability were carefully monitored throughout the study. Immunogenicity samples were collected from all subjects at Day -3, Day 1, Day 7, and Day 28 (± 2 days).

PART B:

In Part B one dose level (36 g) and administration regimens of PB2452 was evaluated in one cohort. Each cohort will include up to 12 subjects randomized in a 3:1 ratio (PB2452:placebo).

This initial cohort of Part B (Cohort 3) pretreated subjects with 180 mg of oral ticagrelor twice daily for 48 hours prior to randomization to a dose and regimen of PB2452 or matching placebo described in a cohort-specific Dosing Memo. The written Dosing Memo provided by the Sponsor to the clinical site described details of the dosing regimen, cohort size, sampling schedules, and other cohort-specific study activities prior to initiation of each cohort. The dose level of the initial regimen in Part B were not exceed twice the total dose level (36 g) shown to be safe and well tolerated in older and elderly subjects (50-80 years) in Part A of this Phase 2A study and in the Phase 1 study of PB2452 in healthy subjects (PB2452-PT-CL-0001).

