3.3. Treatments

Study Drug will refer to PB2452 or matching placebo.

PART A:

PB2452: PB2452 IV infusion, prepared according to the Pharmacy Manual, was administered on Day 1 for up to 48 hours. The total dose for each subject was 18g. The infusion rate was not to

exceed 18g over 30 minutes and the concentration was not to exceed 24g in 250mL. Subjects were not to receive more than 250 mL of study drug infusion within any 1-hour period. Two cohorts were enrolled in Part A, both at a total dose of 18g.

For each cohort, the dose, infusion rate, and duration was communicated from the Sponsor to the study site, PPD, in a Dosing Memo issued prior to initiation of each treatment cohort.

Matching Placebo: 0.9% sodium chloride single IV infusion, administered on Day 1, was delivered at a rate and volume matching the active infusion.

Ticagrelor: Ticagrelor 90 mg oral tablet (immediate release) administered as 180 mg (2 × 90 mg tablets) loading dose plus 90 mg every 12 hours for 4 additional doses.

ASA: During Screening, starting on Study Day -7, subjects received ASA (enteric coated) 81 mg QD to be taken through to the morning of Day 1, prior to receiving study medication. Subjects who were already taking ASA daily before entering the study must have been willing to document self-administered daily 81 mg dose of ASA between Day -7 and -3, accept ASA 81 mg administered at the clinical site between Day -2 and Day 1, and suspend further ASA doses until discharge from the clinical facility.

PART B:

PB2452: PB2452 IV infusion, prepared according to the Pharmacy Manual, was administered on Day 1 for up to 48 hours. For each cohort, the dose, infusion rate, and duration was communicated from the Sponsor to the study site, PPD, in a Dosing Memo issued prior to initiation of each treatment cohort. One cohort in Part B was enrolled, at a total dose of 36 g.

Matching Placebo: 0.9% sodium chloride single IV infusion, was delivered at a rate and volume matching the active infusion.

Ticagrelor: Ticagrelor 90 mg oral tablets (immediate release) was administered as a 180 mg (2 × 90 mg tablets) oral dose every 12 hours for 5 total doses.

4. General Statistical Considerations

All statistical analyses will be conducted using statistical analysis system SAS® Version 9.4 or higher (SAS Institute, Cary, NC). For tables and data listings with no data, titles and footnotes will be presented, and “No data to display” will be presented.

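### The Part B protocol sets two different ceilings on total PB2452 dose, 30 g and 36 g, and the only Part B cohort is reported at 36 g (36 mg in one SAP list)

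*Protocol*

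**What the plan says.** **Part B protocol.** The PB2452 paragraph of the synopsis, under study drug, dosage and route, says: "The total dose for each subject will not exceed 30 g". It also limits the infusion rate, the concentration and the volume per hour. The synopsis design section says: "The dose level of the initial regimen in Part B will not exceed twice the total dose level (36 g"), and section 3.1 repeats this. Both add that cohorts after Cohort 3 may go higher. Section 3.4.2 gives no total-dose, rate, concentration or volume limit; those details are left to instructions sent "in a Dosing Memo issued prior to initiation of each treatment cohort".

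**Part A protocol.** The synopsis and the body agree. Section 3.4.2 says: "The total dose for each subject will not exceed 30g", with the same rate, concentration and volume limits as the Part A synopsis.

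**SAP.** Section 3.1 gives the 30 g maximum under Part A only: "The maximum total dose of PB2452 administered to any subject as not to exceed 30g". For Part B it says: "In Part B one dose level (36 g) and administration regimens of PB2452 was evaluated in one cohort". Section 3.3 agrees: "One cohort in Part B was enrolled, at a total dose of 36 g". Section 3.1 adds that no cohort followed Cohort 3. The treatment-group list in section 4 labels Cohort 3 as 36 mg.

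**The concern.** A maximum total dose per subject is a safety limit, and the Part B synopsis gives two values for it a few pages apart. The dose actually reported lies between them: within one ceiling and above the other.

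The practical consequence is the classification of Cohort 3. Part B section 6.2.2 defines a deviation as a departure from the design or procedures in the protocol, and treats as important one that might significantly affect subject safety. SAP section 5.2 lists deviations by Part. If 30 g was the limit, PB2452 recipients who received more than that belong in the listing. If 36 g was the limit, they do not. The protocol text gives no means of deciding.

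The 36 mg label is a smaller matter, but it sits in the list of groups that the summaries use by default, so it could carry into output headings.

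**Working it through.** **Inputs**

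- 18 g: the highest Phase 1 dose (Part B protocol, section 1.1.2) and the total dose in both Part A cohorts (SAP section 3.3).
- 30 g: Part B synopsis, PB2452 dosage paragraph.
- 36 g: Part B synopsis design section, Part B section 3.1, and SAP sections 3.1 and 3.3.
- Cohort of up to 12, randomised 3:1: Part B section 3.1.
- 36 mg: SAP section 4, treatment-group list.

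**The plan's own figure.** Twice the earlier dose is 2 × 18 g = 36 g. The stated ceiling reproduces, so it is not a misprint for another number.

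**The two ceilings compared**

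- Excess: 36 − 30 = 6 g, and 6/30 = 20%.
- Largest multiple of 18 g that 30 g allows: 30/18 = 1.67. A regimen at twice the earlier dose cannot be given under the 30 g limit.
- Fraction of an assigned 36 g that stays within 30 g: 30/36 = 83.3%. Only a subject who received no more than this fraction would be within the lower limit.
- PB2452 recipients affected: at most 12 × 3/4 = 9. This is an upper bound; the actual size of Cohort 3 is not given.

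**Where each limit stands**

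| Limit | Part A synopsis dosage paragraph and 3.4.2 | Part B synopsis dosage paragraph | Part B synopsis design and 3.1 | Part B 3.4.2 |
|---|---|---|---|---|
| Total dose | 30 g | 30 g | 36 g (initial regimen) | none |
| Duration | 48 h | 48 h | 48 h | 48 h |
| Rate | 18 g per 30 min | 18 g per 30 min | none | none |
| Concentration | 24 g in 250 mL | 24 g in 250 mL | none | none |
| Volume in any hour | 250 mL | 250 mL | none | none |

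If the Part B dosage paragraph is discounted as text carried over from Part A, the rate and hourly-volume limits go with it, because Part B states them nowhere else. Concentration is different. Part B section 3.4.4.1 gives its own range with an upper end of 72 mg/mL, whereas 24 g in 250 mL is 24,000/250 = 96 mg/mL. Those two figures also need reconciling.

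**The label.** 36 mg = 0.036 g, and 0.036/36 = 1/1000 of the dose given in SAP sections 3.1 and 3.3.

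**The case against.** The strongest reply is that the 30 g sentence in the Part B synopsis is a leftover. It matches the Part A synopsis sentence. The Part A design sections state maxima for dose, duration and rate together, while the matching Part B sections keep only the duration limit. Part B section 3.4.2 drops the limits that Part A section 3.4.2 carries, and the SAP states 30 g under Part A only. This pattern is real and makes a carry-over plausible. It does not settle the matter: both figures stand in the current Part B text, no passage says that one replaces the other, and no rule says that the body overrides the synopsis, which itself contains both. The SAP cites Part B version Final 1.0 and, in section 13, reports no change from the protocol.

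One could also say that two upper bounds can hold together. They can, but then the lower one binds and 36 g exceeds it.

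Three further points stand and limit the consequences. Under Part B section 6.2.2 the clinical monitor documents deviations, so a listing can be produced from those records; what is undetermined is whether a Cohort 3 dose above 30 g should have been recorded as one. No population that the SAP defines excludes subjects for deviations, so no planned PD, PK or safety estimate is shown to change. And the total-dose ceiling is not the only dose control in Part B: section 1.3 requires modelled exposure to stay within the rat no-adverse-effect exposures, and section 3.4.2.1 requires committee review before escalation.

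**Conclusion.** The concern holds. The current Part B protocol contradicts itself on the maximum total dose per subject, and the only dose reported for Part B is 20% above the lower figure. As a result, the deviation status of up to 9 PB2452 recipients cannot be determined from the protocol and SAP. The count assumes a full cohort of 12 split exactly 3:1, and the excess assumes that subjects received their assigned 36 g; the Cohort 3 Dosing Memo and the actual doses are not in the documents. The effect is on a safety limit and on deviation reporting, not on a planned estimate. The 36 mg label is a plain unit error within the SAP. This review takes no position on which ceiling is right.

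**What to change.** 1. Reconcile the Part B synopsis design section, the synopsis dosage paragraph, section 3.1 and section 3.4.2 so that Part B states one total-dose limit throughout. Say whether the rate, concentration and hourly-volume limits in the dosage paragraph apply to Part B, and reconcile its 96 mg/mL with the 72 mg/mL in section 3.4.4.1.
2. Record which total-dose limit was in force when Cohort 3 was dosed, and on what authority.
3. If it was the 30 g limit, compare each subject's recorded dose with 30 g and show those above it in the Part B listing under SAP section 5.2. The data exist: Part B section 3.4.6 says that the "actual dose received of study drug and matching placebo infusion and ticagrelor dosing will be recorded on the appropriate pages of the eCRF".
4. Correct the Cohort 3 label in SAP section 4 so that it agrees with SAP sections 3.1 and 3.3.

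The cost is a protocol clarification, a recorded statement of the limit that applied and a one-word SAP correction. The SAP describes Cohort 3 as already enrolled, so the clarification cannot alter that cohort's dosing; its value is in correct classification and reporting. No further subjects or data are needed.

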### **Matching Placebo:**

0.9% sodium chloride single IV infusion, to be delivered at a rate and volume matching the active infusion.

### **Ticagrelor:**

Ticagrelor 90 mg oral tablets (immediate release) will be administered as a 180 mg ( $2 \times 90$  mg tablets) oral dose every 12 hours for 5 total doses.

## **STATISTICAL METHODS:**

### **Sample Size:**

The sample size (N) of up to 3 cohorts for Part B of this study is based on clinical and practical considerations and not on a formal statistical power calculation. The sample size will provide preliminary safety, efficacy and PK information in a dose/regimen finding fashion.

### **Analysis Populations:**

- The *Safety Population* will include all subjects who receive any amount of study drug.
- The *PK Population* will include subjects in the safety population who have  $\geq 1$  measurable PK concentration.
- The *PD Population* will include subjects in the safety population who receive  $\geq 1$  dose of ticagrelor and have  $\geq 1$  measurable post dose PRU value.

### **Safety Analyses:**

Adverse events will be coded by preferred term and system-organ-class (SOC) using the latest version of the Medical Dictionary for Regulatory Activities (MedDRA). All AE data will be presented in Data Listings. Treatment-emergent AEs (TEAEs) will be summarized by treatment and overall, as well as by severity and relationship to study drug. All SAEs and AEs leading to discontinuation of study drug will be presented in the Data Listings.

Actual values and changes from Baseline in clinical laboratory test results, vital sign measurements, and 12-lead ECG results will be summarized by treatment at each time point using descriptive statistics (number of subjects, mean, standard deviation [SD], median, minimum, and maximum). Clinical laboratory test results, vital sign measurements, 12-lead ECGs, Holter monitor report data, immunogenicity results, and physical examination findings will be presented in Data Listings.

### **Efficacy Analyses:**

Pharmacodynamic data will be summarized using descriptive statistics (number of subjects, mean, SD, CV, median, minimum, and maximum) for each treatment group or by cohort at each time point

if applicable. Inferential analysis maybe carried out to compare the % inhibition of PRU, LTA, PRI between PB2452 vs Placebo individually. However due to the limited sample size, efficacy analysis results will be considered descriptive.

**Pharmacokinetic Analyses:**

Plasma concentrations will be listed and summarized descriptively (number of subjects, arithmetic mean, SD, coefficient of variation [CV], median, minimum, and maximum). Plasma concentration versus time profiles for each subject will be presented graphically. The mean plasma concentration versus scheduled time profiles will be presented graphically by dose.

Pharmacokinetic parameters will be summarized by time point for each dose level using descriptive statistics (number of subjects, mean, SD, CV, median, minimum, and maximum). Geometric means will be reported for AUCs and  $C_{max}$ .

## LIST OF ABBREVIATIONS AND DEFINITIONS

---

AA	arachidonic acid
ACS	acute coronary syndrome
ADA	anti-drug antibodies
ADP	adenosine diphosphate
AE	adverse event
Ae 48	total amount of drug excreted in urine at 48 hours after dosing
Ae 24	total amount of drug excreted in urine at 24 hours after dosing
Ae t1-t2	Ae from time t 1 to t 2 hours
Ae t1-t2	Ae from time t 1 to t 2 hours
ALP	alkaline phosphatase
ALT	alanine aminotransferase
aPTT	activated partial thromboplastin time
ASA	acetylsalicylic acid, aspirin
AST	aspartate aminotransferase
AUC	area under the plasma concentration versus time curve
AUC 0-12	AUC from time zero to 12 hours after dosing
AUC 0-24	AUC from time zero to 24 hours after dosing
AUC 0-48	AUC from time zero to 48 hours after dosing
AUC 0-∞	area under the plasma concentration versus time curve from time zero extrapolated to infinity
AUC 0-τ	area under the concentration versus time curve from time zero to the time of the last quantifiable concentration
bid	twice daily
BL	baseline
BLQ	below the limit of quantification
BMI	body mass index
BP	Blood Pressure
Bpm	beats per minute
BUN	Blood Urea Nitrogen
CABG	coronary artery bypass graft
CFR	Code of Federal Regulations
CL	clearance
CLR	renal clearance
C max	observed maximum plasma concentration
CrCl	creatinine clearance
CS	clinically significant
CSR	Clinical Study Report

CTCAE	Common Terminology Criteria for Adverse Events
CV	coefficient of variation
CYP3A	cytochrome P450 3A4
DAPT	dual antiplatelet therapy
DBP	diastolic blood pressure
DLT	dose-limiting toxicity
ECG	electrocardiogram
eCRF	electronic case report form
eGFR	estimated glomerular filtration rate
ELISA	enzyme-linked immunosorbent assay
EOS	end of study
FDA	Food and Drug Administration
Fe 24	Fraction excreted in urine from 1 to 24 hours after dosing
Fe 48	fraction excreted in urine from 1 to 48 hours after dosing
FSH	follicle stimulating hormone
GCP	Good Clinical Practice
GGT	gamma-glutamyl transferase
GI	gastrointestinal
GLP	Good Laboratory Practice
HbA1c	glycosylated Hemoglobin Hgb
HBsAg	hepatitis B surface antigen
HCV	hepatitis C virus
HDL	high-density lipoprotein
Hgb	hemoglobin
HIV	human immunodeficiency virus
HR	resting heart rate
HTN	hypertension
IB	Investigators' Brochure
ICF	informed consent form
ICH	International Council for Harmonisation
INR	international normalized ratio
IPA	inhibition of platelet aggregation
IRB	institutional review board
IRR	infusion-related reaction
IV	Intravenous- (ly)
LDH	lactate dehydrogenase
LDL	low-density lipoprotein

LTA	light transmittance aggregometry
MAP	mean arterial pressure
MCH	mean corpuscular hemoglobin
MCHC	mean corpuscular hemoglobin concentration
MCV	mean corpuscular volume
MDMA	methylenedioxymethamphetamine
MDRD	Modification of Diet in Renal Disease
MedDRA	Medical Dictionary FOR Regulatory Activities
MI	Myocardial infarction
MPV	Mean platelet volume
msec	millisecond
MTD	maximum tolerated dose
N	sample size
NCS	not clinically significant
NOAEL	no adverse effect level
OTC	Over the counter
PD	Pharmacodynamic
PEF	Peak expiratory flow
PK	pharmacokinetic
PO	by mouth
PRI	platelet reactivity index
PRU	P2Y 12 reaction units
PT	prothrombin time
PTT	partial thromboplastin time
QD	once daily
QTcF	Fridericia-corrected QT interval
RBC	red blood cell(erythrocyte)
RR	respiration rate
SAE	serious adverse event
SAP	statistical analysis plan
SBP	systolic blood pressure
SD	standard deviation
SOC	System- organ- class
SOP	standard operating procedure
SpGr	specific gravity
SRC	Safety Review Committee
t 1/2	terminal elimination half-life
TAM	ticagrelor active metabolite AR-C124910XX
TEAE	treatment-emergent adverse event

$T_{max}$	time to reach the observed maximum (peak) concentration
TRAP	thrombin receptor activating peptide
TSH	thyroid stimulating hormone
ULN	upper limit of normal
US	United States
VASP	vasodilator-stimulated phosphoprotein
WBC	white blood cell

